Aim 2. Identify theory-based variables (attitudes, self-efficacy, perceived barriers, and social influences related to breast cancer survivorship) that **mediate** the intervention effects of the TICAA on the primary outcomes of the TICAA from baseline to Time Point 1.

Aim 3 (exploratory). Explore whether the effects of the TICAA on the primary outcomes are **moderated** by background factors and disease factors.

Study Design

Organizational structure of the study team:

This is a PI initiated R01 research project that is funded by the National Cancer Institute (National Institute of Health). Due to PI's move from Duke University to Emory University, the study is being transferred from Duke Univ. to Emory University. This is the fourth year of the total 5 year of funding. This IRB approval is needed for the grant transfer.

The study team includes the PI, 1 Co-Investigator, 1 Statistician, multiple Consultants, 3 interventionists and 1 or 2 research assistants. Except the consultants, all research team members will be Emory affiliated. The research team will conduct the study at School of Nursing, Emory University.

Setting and location:

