Aim #1: Effects on Primary Outcomes. Separate intent-to-treat general linear models 86 will be used to examine differences in continuous outcome measures by intervention group at each time point, adjusting for baseline outcome and any variables that demonstrate imbalances in preliminary analyses. Model assumptions will be assessed, and modifications will be implemented as necessary to improve mode fit. Differences in continuous outcome measures over time will be examined using an intent-to-treat linear mixed-model growth curve analysis with SAS Proc Mixed.86 Mixed models will be used in which all available data collected during follow-up is used.87,88 Separate mixed effects regression models will be generated for each outcome measure. Both random slopes and intercepts will be modeled to represent the subject level deviation from the average, or fixed-effect, slope over time and intercept, respectively. Restricted maximum likelihood estimation will be used, and the most appropriate covariance structure will be examined. The outcomes will be analyzed as repeated observations of the dependent variables, with mean-centered baseline outcome scores serving as a covariate. Other predictors will include intervention group, time from baseline to follow-up, the interaction of group and time, and the interaction of baseline measures and time. Baseline outcome and group will be analyzed as time-independent covariates. Other demographic or treatment timeindependent variables identified in preliminary analyses may be included as covariates. Main effects and higher order interaction terms will be examined. The Akaike information criterion will evaluate overall model fit and to select the best-fitting longitudinal change pattern.89

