Aim #2: Mediation of Intervention effects. Sequential process random regression growth curve modeling90 will be performed to explore the hypotheses that attitudes, self-efficacy, perceived barriers, and social influences, separately, mediate the relationship between intervention group and change over time in primary outcomes. Specifically, we will examine whether the women who receive the TICAA show more favorable changes on the mediators at post-intervention and the follow-up periods relative to pre-intervention than do those in the control group. Mediational analyses will be performed to examine whether there is statistical support for the view that the putative mediator variables actually mediate effects of the TICAA on participants' needs for

help, physical and psychological symptoms, and quality of life. Although various methods are appropriate for evaluating mediation in this setting, random regression growth curve modeling90 was chosen as it prospectively and longitudinally tests the three criteria of mediation proposed by Baron and Kenny. 91 Modeling will rely on incorporating time varying [mediator] as a predictor of outcome in each sequential assessment. To test the mediation hypothesis, individual slope and intercept parameters will be estimated for each participant based on intervention, mediator, and outcome. The intercept parameters will be coded to represent the value of the linear growth trajectory for each participant at baseline. The sequential process, or lagged approach, will allow for stronger inference regarding causality. Model assumptions will be assessed, and transformations will be applied as necessary. A series of four regressions will be used to test each of the mediational chains according to the criteria specified by Baron and Kenny.91 Significant decreases in outcome will be assessed using the Sobel test. 92

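### Aim 2 stops at month 1, where mediator and outcome appear to be measured together, so the lagged, more causal reading promised for the mediation analysis does not hold in that window; the Aim 2 statement and its analysis section also disagree on which surveys are used

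*Combined protocol and SAP*

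**What the plan says.** All references are to the combined protocol and SAP.

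- **Goals/Aims, Aim 2** asks which theory-based variables mediate "the intervention effects of the TICAA on the primary outcomes of the TICAA from baseline to Time Point 1". Aim 1 defines Time Point 1 as 1 month (primary) and Time Point 2 as 3 months (secondary).
- **Procedures for data collection** describes three surveys: one at enrollment before program use, one due by the end of month 1 and one due by the end of month 3. Outcome and mediator scales appear in one list of instruments, with no timetable by scale.
- **Aim #2: Mediation of Intervention effects** looks for "more favorable changes on the mediators at post-intervention and the follow-up periods relative to pre-intervention" and enters the time-varying mediator "as a predictor of outcome in each sequential assessment". It then states: "The sequential process, or lagged approach, will allow for stronger inference regarding causality".
- The same section specifies individual growth parameters: "The intercept parameters will be coded to represent the value of the linear growth trajectory for each participant at baseline". The Aim #1 section instead treats the pre-test as an adjustment variable, "with mean-centered baseline outcome scores serving as a covariate".
- On the test itself, the Aim #2 section says: "Significant decreases in outcome will be assessed using the Sobel test".

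**The concern.** A lagged mediation analysis needs a mediator measured after the intervention starts and before the outcome. If Aim 2 really ends at month 1, the design supplies no such pair, and a month-1 result could be reported as lagged when it is concurrent. Any non-causal correlation between two self-reports completed in one sitting would then count toward the apparent mediation.

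If the analysis section governs instead, month 3 is in play and a lag is available. But the stated aim is then wrong, and the reader still cannot tell which mediator survey predicts which outcome survey. Leaving this open matters more because 210 of the 330 women have already completed participation, so the choice could in principle be made with their data in hand.

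**Working it through.** **1. Pairs available, by window**

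| Mediator survey | Outcome survey | In the Aim 2 window? | What it offers |
|---|---|---|---|
| Baseline | Month 1 | Yes | Lagged, but the mediator predates program use and cannot carry its effect |
| Month 1 | Month 1 | Yes | Concurrent, no lag |
| Month 1 | Month 3 | No | The first usable lag |

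That the month-1 scales share one survey is an inference from the single set of instruments. No schedule by scale is given.

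**2. Growth model on two surveys**

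A random intercept and slope model has four variance parameters: intercept variance P, covariance C, slope variance S and residual E. Months 0 and 1 give three moments:

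- Var(0) = P + E
- Cov(0,1) = P + C
- Var(1) = P + 2C + S + E

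Two different sets (P, C, S, E) give the same moments:

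- (0.70, -0.05, 0.20, 0.30): 1.00; 0.65; 0.70 - 0.10 + 0.20 + 0.30 = 1.10
- (0.85, -0.20, 0.50, 0.15): 1.00; 0.65; 0.85 - 0.40 + 0.50 + 0.15 = 1.10

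So the unrestricted variances are not identified from two surveys. With months 0, 1 and 3 there are six moments and the sets separate: Var(3) = P + 6C + 9S + E is 2.50 for the first and 4.30 for the second. Arm effects and the marginal covariance can be estimated either way.

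**3. Illustrative size at month 1**

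The plan gives no power or path size for Aim 2, so there is no planned figure to reproduce.

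- *From the documents:* 165 per arm and 35% attrition, hence 165 x 0.65 = 107. The 35% is stated for month 3, so month-1 numbers may be larger.
- *Assumed:* arm effect on the mediator a = 0.5 residual SD; no causal path from mediator to outcome; same-survey residual correlation r; baseline correlation 0.3; carry-over 0.6; 5% level.

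The spurious indirect effect is a x r = 0.05/0.10/0.15 for r = 0.1/0.2/0.3. Expected test sizes by hand:

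- z_a = 0.5 / sqrt(2/107) = 3.66
- z_b = r / sqrt((1 - r²)/209) = 1.45/2.95/4.55, where 209 = 214 - 5 coefficients
- Sobel z = z_a z_b / sqrt(z_a² + z_b²) = 1.35/2.30/2.85, against a cut-off of 1.96

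Simulated false mediation rates agree with this:

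| Rule | r = 0.1 | r = 0.2 | r = 0.3 |
|---|---|---|---|
| Sobel alone | 16% | 63% | 91% |
| Also requires arm effect on outcome; true effect 0 | 1% | 3% | 4% |
| Same rule; true effect 0.25 SD | 7% | 27% | 43% |
| Same rule; true effect 0.5 SD | 15% | 62% | 87% |

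**4. Month-1 mediator to month-3 outcome, adjusted for month-1 outcome**

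Further assumptions: direct effect 0.25, outcome persistence 0.5, month-3 noise variance 0.75, Sobel alone.

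- If month-1 outcome captures all the shared correlation, false mediation is about 2% at each r.
- If the mediator residual also correlates 0.05/0.1/0.2 with month-3 noise, it is about 5/15/62%.

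**The case against.** **The analysis section may govern.** It is the operative text, it points beyond month 1, and the trial as a whole does contain a usable lag. This stands. A reader might infer that lagged mediation is impossible in this trial, or that the method is invalid. The documents do not support that. The fault lies in the stated window and the missing pairing. Even if the analysis section governs, the aim must be edited and the pairing stated.

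**Sobel alone is not the planned procedure.** The plan says: "A series of four regressions will be used to test each of the mediational chains". This also stands, which is why the rates that require an arm effect on the outcome are shown. They assume that such an effect is one of the criteria. They range widely with r and with the program's effect, and no value in the documents anchors either. They show that the risk is small if the program leaves the outcome unchanged and can be large if it does not. They do not measure it.

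**The lagged model is not generally safer.** A reader might set about 2% against 16/63/91% and conclude that it is. The 2% follows from letting month-1 outcome absorb all the shared correlation. A stable trait that affects every self-report would break that assumption, as step 4 shows.

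**Two further overreadings.** Someone might infer that the surveys were chosen after results were seen. The plan says only that 210 women completed participation, not that outcomes were examined. Nor does the two-survey variance problem make Aim 2 inestimable. It arises only if an unrestricted growth model is fitted to two surveys, and the baseline-as-covariate rule is written for Aim 1.

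**Conclusion.** The point holds for Aim 2 only. Within baseline to month 1, the claim of a lagged approach with stronger causal inference describes a property that the design lacks, and the aim and its analysis section conflict on the surveys used. This rests on the month-1 mediator and outcome scales being completed in one survey, which is the natural reading of the data collection section but is not spelled out by scale.

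The rates show direction under assumed correlations and path sizes; they are not estimates for this trial. No general superiority of the month-1-to-month-3 analysis is claimed. The Aim 1 efficacy analyses are untouched. The change should be made, but it does not threaten the trial's main conclusion.

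**What to change.** Reconcile the Aim 2 statement with its analysis section in one of two ways, or do both under separate labels.

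**(a) Keep Time Point 1.** Regress month-1 outcome on arm, month-1 mediator, baseline mediator and baseline outcome. Label the result concurrent and remove the lag and causality wording. Do not fit an unrestricted random intercept and slope model to two surveys.

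**(b) Extend Aim 2 to Time Point 2.** State the pairing: month-1 mediator to month-3 outcome, adjusted for arm, baseline mediator, baseline outcome and month-1 outcome.

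In either case, date the change relative to access to outcome data. As a minor edit, say that the Sobel test is for the indirect effect, not for decreases in outcome.

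**Cost.** Text edits only. Both follow-up surveys are already scheduled, so no visit or instrument is added.

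**Downsides of (b).** Attrition may reach 35% by month 3. Mediation already complete by month 1 is missed: with true paths of 0.5 and 0.3 it is found in about 2% of simulated trials. A delayed mediator-to-outcome path of 0.2 is found in about 75% at 107 per arm (Sobel alone, 5% level). The estimate stays biased if a shared source of correlation persists to month 3.

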A technology-based approach using computers and mobile devices (smart phones and tablets) promises to meet this necessity with high flexibility and accessibility, and minimizes the cost of the intervention in busy health care settings. Also, a technology-based intervention that does not involve face-to-face interactions could work better for many women from cultures where breast cancer is still a stigmatizing experience. Bespite the high potential, few technology-based interventions are available for ethnic minority breast cancer survivors, especially for Asian Americans. Therefore, based on Preliminary Studies (PSs), the research team has developed and pilot-tested a theory-driven technology-based information and coaching/support program that: (a) is tailored to Asian American breast cancer survivors by incorporating actual data on individual sub-ethnic groups cultural attitudes from PSs; (b) uses multiple languages; (c) provides both group and individual (real-time and personalized) coaching/support by culturally matched bilingual health care providers; (d) incorporates peer support through a social media function; and (e) integrates existing general and culture-specific evidence-based educational content from scientific authorities. Among over 71 sub-ethnic

groups of Asian Americans,⁴⁶ only three sub-ethnic groups (Chinese, Korean, and Japanese) were selected for the program development for the convenience of the approach (e.g., language). Within Asian Americans, Chinese are the largest sub-ethnic group,^{47,48} Koreans are the fastest growing sub-ethnic group,^{47,48} and Japanese are the sub-ethnic group at the highest risk of breast cancer.^{1,2,11,49}

Goals/Aims

The purpose of the proposed randomized intervention study is to test the efficacy of the technology-based information and coaching/support program for Asian American breast cancer survivors (TICAA) in enhancing the women's breast cancer survivorship experience.

The **specific aims** of the study are to:

Aim 1. Determine whether the intervention group (who uses the TICAA and the information on breast cancer by the American Cancer Society [ACS]) will show significantly greater improvements than the control group (who uses only the information on breast cancer by the ACS) in **primary outcomes** of the TICAA (needs for help, physical and psychological symptoms, and quality of life) from baseline (pre-test) to Time Points 1 (post 1-month; primary) and 2 (post 3-months; secondary).

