The data are mainly collected through the Internet survey questionnaire. When potential participants visit the project Web site (after receiving/reviewing a study announcement), they will be asked to review the informed consent. When participants click I agree to participate, they will have given their consent. Then, after checking them against the inclusion criteria and quota requirements, only those who meet the criteria and requirements will be automatically assigned a serial number, and randomized into two groups using an automated random number generator accessible through the Web site.

Then, the women will be asked to fill out the Internet survey questionnaire (if requested, paper-and-pencil questionnaires will be provided/used, or research staff will assist in administering the Internet surveys over the phone.) and sign up the Web site by creating their own ID and passwords. Whenever they visit the Web site, they need to use the ID and passwords to log in the site. If they want, they can change their ID and passwords. Then, both groups will be provided with an electronic instruction sheet on when they need to come back and fill out additional questionnaires and/or use the program.

Biweekly, the research team will send reminders and thank-you emails. Two weeks before the end of the 1st month, both groups will be asked to fill out the next set of the instruments by the end of the 1st month. Then, 2 weeks before the end of the 3rd month, both groups will be asked to fill out the next set of the instruments by the end of the 3rd month.

O Description of research instruments to be used (e.g., questionnaires, surveys, interview or focus group guides, scales)

Multiple instruments will be used: the Support Care Needs Survey-34 Short Form (SCNS-34SF),⁵⁰ the Memorial Symptom Assessment Scale-Short Form (MSAS-SF),⁵¹ the Functional Assessment of Cancer Therapy Scale-Breast Cancer (FACT-B),⁵² the modified Questions on Attitudes, Self-Efficacy, Perceived Barriers, and Social Influences (QASPS),⁵³ the Cancer Behavior Inventory (CBI),^{54,55,56} the Perceived Isolation Scale (PIS),^{57,58} the Personal Resource Questionnaire (PRQ-2000),⁵⁹ and 27 questions on background characteristics, level of acculturation, and disease factors. The reliability and validity of all the instruments have been established among Asian Americans. Cronbach's alpha of individual instrument ranged from .76 to .96 among Asian Americans.

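### The Aim 2 plan attaches the Sobel test to a decrease in outcome, which that test does not assess and which is the wrong direction for quality of life; the indirect effect should be named and given a better interval

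*Combined protocol and SAP*

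**What the plan says.** All references are to the combined protocol and SAP.

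- **Data analysis plan, Aim #2 (Mediation of Intervention effects).** The hypotheses are that each of four variables (attitudes, self-efficacy, perceived barriers, social influences) separately acts to "mediate the relationship between intervention group and change over time in primary outcomes". The outcomes covered are participants' needs for "help, physical and psychological symptoms, and quality of life".
- **Same section, the test.** "A series of four regressions will be used to test each of the mediational chains according to the criteria specified by Baron and Kenny". The next and closing sentence is "Significant decreases in outcome will be assessed using the Sobel test". The section never mentions an indirect effect, and it makes no exception or reverse scoring for quality of life.
- **Same section, the mediators.** The question is whether women using the programme "show more favorable changes on the mediators at post-intervention and the follow-up periods relative to pre-intervention". This wording is direction-neutral.
- **Goals/Aims, Aim 1.** The primary outcomes are "needs for help, physical and psychological symptoms, and quality of life", and the intervention group "will show significantly greater improvements than the control group". This too is direction-neutral.
- **Description of research instruments.** The scales are listed, including "the Functional Assessment of Cancer Therapy Scale-Breast Cancer (FACT-B") for quality of life, with no scoring direction for any of them.

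**The concern.** Two things in the closing sentence do not fit together.

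First, the quantity. A decrease in outcome is a statement about the outcome itself. The Sobel statistic is a statement about the product of two regression paths. Either can be significant without the other, so the sentence does not say what Aim 2 will estimate.

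Second, the direction. In the ordinary meaning of the constructs, benefit is a fall in needs for help and in symptoms, but a rise in quality of life. Only this sentence fixes a direction, and it fixes the same one for every outcome.

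A further matter is the choice of test. Sobel treats the product of two estimates as normal. That product is skewed when the paths are modest, and the test then rejects too seldom.

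At stake is Aim 2, one of the two aims not labelled exploratory. An analyst must guess the estimand, possibly after seeing results, and real mediation may be missed.

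**Working it through.** **Inputs.** From the sample-size paragraph (Recruitment): 105 per group, so 2 × 105 = 210 women; 330 enrolled; 35% attrition by Time Point 2, and 330 × 0.65 = 214.5. From Goals/Aims: Aim 2 runs from baseline to Time Point 1. The analysed number therefore lies between about 210 and 330. The documents attach no figure to the mediation test, so there is none to reproduce. Path sizes and the two-sided 0.05 level are assumptions; the plan's 0.00625 is set for group main effects.

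**Step 1: what Sobel tests.** Let *a* be the group effect on the mediator, *b* the mediator's effect on the outcome given group, *c* the group effect on the outcome, and *c′* that effect after adding the mediator.

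z = ab / √(a²·SE_b² + b²·SE_a²)

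In linear regression on the same women, ab = c − c′. In simulation (n = 214, 4,000 runs per setting) this held in every run. Sobel therefore tests the drop in the group effect, not a drop in the outcome.

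**Step 2: the two findings come apart.** Same simulation:

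| Setting | Sobel significant | Mean outcome falls significantly |
|---|---|---|
| Outcome falls, no mediation (a = 0.5, b = 0, c′ = −0.5, common shift −0.5) | 1.8% | 100% |
| Mediated fall (a = 0.5, b = −0.5) | 94.2% | 36.8% |
| Mediated rise (a = 0.5, b = +0.5) | 94.4% | 0.0% |
| Mediation offset by an opposing direct effect (a = 0.5, b = −0.5, c′ = +0.25) | 94.6% | 2.2% |

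The first and last rows show the mismatch. The middle rows show that two-sided Sobel works equally well in either direction.

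**Step 3: why Sobel is conservative, by hand.** Take n = 210 in two equal arms, unit error variance, a = 0.5 and b = 0.20.

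- SE_a = √(4/210) = 0.138, so a/SE_a = 3.62.
- SE_b = √(1/210) = 0.069, so b/SE_b = 2.90.
- z = 0.10 / √(0.25 × 0.00476 + 0.04 × 0.01905) = 0.10 / 0.0442 = 2.26.

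Both paths are clearly different from zero, yet the expected Sobel z only just passes 1.96. Approximate power is Φ(2.26 − 1.96) = Φ(0.30) = 62%.

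**Step 4: Sobel against an interval that respects the product distribution.** Simulated power, two-sided 0.05:

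| a, b | n = 210 | Gap (points) | n = 330 | Gap (points) |
|---|---|---|---|---|
| 0.5, 0.20 | 61% vs 76% | 15 | 91% vs 95% | 4 |
| 0.5, 0.25 | 80% vs 90% | 10 | 98% vs 99% | 1 |
| 0.4, 0.20 | 45% vs 65% | 20 | 81% vs 89% | 8 |

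Repeat runs agree within a few points; the last gap is 8 to 9. With a = b = 0.5 at n = 210, Sobel and the percentile bootstrap give 93% and 94%, so little is lost. With no group effect on the mediator and b = 0.3, false positives are about 2.5 to 3% for Sobel and about 5% for the product-distribution interval.

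**The case against.** The strongest reply is that the sentence is a slip and its meaning is recoverable. It follows directly on the Baron and Kenny regressions, where the natural thing to decrease is the group effect once the mediator is added. Sobel is a standard test of that drop, and on this reading the direction problem disappears. This is probably what was meant. It stands as a limit on the harm but not as a defence of the text, which says outcome and never defines the indirect effect.

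A reader might go further and infer that a mediated gain in quality of life could never be declared. The documents do not support this. They contain no one-sided mediation rule, Sobel itself is sign-neutral, and the four regressions also enter the assessment. The 0.0% in Step 2 describes a fall in the outcome, not a success rule in the plan. Nor does the word decreases govern the mediators, which have their own direction-neutral wording.

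On power, Sobel is a legitimate if conservative choice, and the loss depends on paths that the documents do not give. The simulation uses a single mediator and ordinary regression, whereas the plan uses lagged growth curves with random slopes. 210 is also the low end for an analysis to Time Point 1. All of this stands, so the percentages indicate the direction and rough size of the loss and do not forecast it. Finally, the section describes the analysis as exploring hypotheses, which lowers the consequence.

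**Conclusion.** The concern holds as a modest defect of wording, estimand and method in Aim 2. The closing sentence pairs the Sobel test with a quantity that it does not test and, read literally, with a direction that is worsening for quality of life. The direction point rests on the ordinary meaning of the constructs, since no scoring is given.

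Separately, the product-distribution interval is the better tool. Under assumed paths of 0.4 to 0.5 SD for the mediator shift and 0.20 to 0.25 for *b*, at two-sided 0.05, Sobel gives up about 10 to 20 points of power at 210 women and about 1 to 9 at 330. It gives up almost nothing when *b* = 0.5. No design figure, and nothing in Aim 1, changes.

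**What to change.** Replace the closing sentence of the Aim #2 section with:

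> For each mediator and outcome, the indirect effect of the intervention through the mediator will be estimated with a two-sided 95% percentile-bootstrap (or Monte Carlo product-distribution) confidence interval. Benefit is a negative indirect effect on needs for help and symptoms and a positive indirect effect on quality of life.

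In the same place, state how this interval and the four regressions together decide whether mediation is claimed.

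**Cost.** There is no change to sample size or conduct. Bootstrapping lagged mixed models, possibly with multiple imputation, for four mediators and several outcomes takes real computing time. The Monte Carlo interval takes less, because it draws from the estimated paths and standard errors without refitting. Sobel's conservatism is lost: false positives move from about 2.5 to 3% to near the nominal 5%.
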